2.2.2 Diagnosis and Main Criteria for Inclusion

Adolescent or adult subjects aged 12 – 65 years are eligible for the study if they have a diagnosis of AD with disease duration of at least 6 months and no change in treatment or severity for at least 4 weeks prior to screening.

At baseline, subjects must have an overall IGA score of 2 (mild) or 3 (moderate) on a 5-point Investigator Global Assessment (IGA) scale, Eczema Area and Severity Index (EASI) score \geq 5, and total body surface area (TBSA) affected of between 2 and 30%.

2.2.3 Study Population Characteristics

Subjects with a clinical diagnosis of AD who meet all the inclusion criteria and none of the exclusion criteria will be eligible to enroll in the study. Detailed inclusion and exclusion criteria are provided in the protocol (see protocol sections 5.1 and 5.2).

2.2.4 Replacement Subjects

No replacement of subjects is allowed for the study.

2.3 TREATMENT AND RANDOMIZATION

2.3.1 Study Medications, Treatment, and Mode of Administration

TER-101 (2.75% w/w) ointment and ointment vehicle will be applied topically twice a day for 28 days, with at least 8 hours between applications. Subjects will apply sufficient study drug to provide a thin covering. A pea-sized amount (approximately 250 mg) should cover approximately 2% body surface area (BSA). Additional instructions on application will be provide in the ‘Instructions for Use’ provided to each subject at randomization.

2.3.2 Randomization

Qualified subjects will be randomly assigned (1:1) to two treatment groups: TER-101 2.75% ointment or vehicle ointment. Blinded study drug will be dispensed on Day 1 (Baseline Visit).

2.3.3 Administration of Treatment

The study medications are for external, topical use on the AD areas twice daily for 28 days.

2.3.4 Duration of Treatment

The duration of the study participation is anticipated to be up to 64 days, including up to 35 days for screening/prior treatment washout and 28 days of study drug treatment. Subjects may be followed for up to an additional 30 days for resolution of AEs after end of treatment.

2.4 ASSESSMENTS

2.4.1 Evaluators

The investigator, a designated and appropriately trained staff member (e.g., sub investigator) or the subject will perform the study assessments according to the defined schedules.

2.4.2 Evaluations – Efficacy

2.4.2.1 Eczema Area Severity Index

The EASI is a scoring system that measures 4 clinical signs, the extent of BSA involved, over 4 separate areas (head/neck, trunk, upper extremities, and lower extremities). Total EASI scores range from 0 to 72.

The 4 clinical signs are:

- Erythema
- Induration/papulation
- Excoriation
- Lichenification

And each feature is graded for each region on a 4-point severity scale of 0 to 3, as below, with:

- 0 = absent
- 1 = mild

- 2 = moderate
- 3 = severe

Half-point scores of 1.5 and 2.5 can also be reported. The investigator or qualified assessor will enter the value for erythema, induration/papulation, excoriation and lichenification and extent of BSA for each region on the electronic case report form (eCRF) page. The EASI score will be calculated by the sponsor/designee. The formulation of the score is as shown below:

Eczema Area and Severity Index (EASI) case report form - age ≥ 8 years

Area of involvement: Each body region has potentially 100% involvement. Score 0 to 6 based on the following table:

% involvement	0	1-9%	10 - 29%	30 - 49%	50 - 69%	70 - 89%	90 - 100%
Region score	0	1	2	3	4	5	6

Severity of Signs: Grade the severity of each sign on a scale of 0 to 3:

0	None
1	Mild
2	Moderate
3	Severe

- ✓ Take an average of the severity across the involved area.
- ✓ Half points (1.5 and 2.5) may be used. 0.5 is not permitted – if a sign is present it should be at least mild [1]

Scoring table:

Body region	Erythema (0-3)	Edema/Papulation (0-3)	Excoriation (0-3)	Lichenification (0-3)	Region score (0-6)	Multiplier	Score per body region
Head/neck	(+)	+	+)	X	X 0.1	
Trunk	(+)	+	+)	X	X 0.3	
Upper extremities	(+)	+	+)	X	X 0.2	
Lower extremities	(+)	+	+)	X	X 0.4	
The final EASI score is the sum of the 4 region scores:							_____
							(0-72)

2.4.2.2 Investigator Global Assessment

The IGA is a 5-point scale that provides a global clinical assessment of overall AD severity based on an ordinal scale. The assessment is static, meaning that the evaluation is done without reference to any other time point.

- 0 = Clear: minor residual hypo/hyperpigmentation; no erythema or induration/papulation; no oozing/crusting.

- 1 = Almost clear: trace faint pink erythema, with barely perceptible induration/papulation and no oozing/crusting.
- 2 = Mild: faint pink erythema with mild induration/papulation and no oozing/crusting.
- 3= Moderate: pink-red erythema with moderate induration/papulation with or without oozing/crusting.
- 4= Severe: deep or bright red erythema with severe induration/papulation and with oozing/crusting.

2.4.2.3 Worst Itch Numeric Rating Scale

The WI-NRS asks subjects to report their worst itch (maximal intensity) during the last 24 hours on an 11-point NRS, ranging from 0 = “no itch at all” to 10 = “worst itch you can imagine”. This will be recorded by the subjects daily in the e-diary.

2.4.2.4 Total Body Surface Area

The TBSA involved with AD will be determined. The subject’s palm and fingers with fingers together represent approximately 1% of the TBSA.

2.4.3 Evaluations – Safety

2.4.3.1 Local Tolerability

The investigator will assess local tolerability by inspecting the application sites for application site erythema and query the subject as to symptoms of burning/stinging or pruritus associated with study drug application. The local tolerability assessment will be conducted at baseline pre-dose and approximately 15 minutes after the first dose, Day 15, and Day 29. The investigator should score the individual components of burning/stinging, pruritus, and erythema based on the average for scores of all application sites.

Grade	Burning/Stinging	Pruritus	Erythema
0 (none)	No stinging/burning	No pruritus	No detectable erythema, skin of normal color
1 (mild)	Slight warm, tingling sensation, not really bothersome	Occasional, slight itching/scratching	Skin pinkness present
2 (moderate)	Definite warm, tingling sensation that is somewhat bothersome	Constant or intermittent itching/scratching which is not disturbing sleep	Definite redness, easily recognized
3 (severe)	Hot, tingling/stinging sensation	Bothersome	Intense redness

2.4.3.2 Adverse Events

AEs or serious AEs (SAEs) occurring in the 30-day period following the last dose of investigational product will be reported, regardless of causality. SAEs occurring after this 30-day period will be reported only if considered related to investigational product or a study-related procedure.

2.4.3.3 Laboratory Sampling

- All study-required laboratory assessments as detailed in the following table and the laboratory manual will be performed by a local laboratory, and confirmation of review of the results must be entered into the electronic case report form (eCRF).
- Additional tests may be performed at any time during the study as determined necessary by the investigator or required by local regulations.
- Tests listed below will be those analyzed descriptively and/or listed.

Hematology	Chemistry	Urinalysis
Platelet Count Red blood cell (RBC) Count Hematocrit Hemoglobin RBC Indices: MCV MCH White blood cell (WBC) count with differential: Neutrophils Lymphocytes Monocytes Eosinophils Basophils	Blood urea nitrogen (BUN) Bicarbonate Calcium Chloride Creatinine Glucose (random) Potassium Sodium Alanine aminotransferase (ALT) Aspartate aminotransferase (AST) Alkaline phosphatase Total bilirubin Total protein Albumin	Specific gravity pH, glucose, protein, blood, ketones, (bilirubin, urobilinogen, nitrite, leukocyte esterase) by dipstick Microscopic examination (if blood or protein is abnormal)
Other Screening Tests	Follicle stimulating hormone (as needed to confirm menopausal status for women of nonchildbearing potential only). Highly sensitive urine human chorionic gonadotropin (hCG) urine pregnancy test (as needed for women of childbearing potential). ^a	
All study-required laboratory assessments will be performed by a local laboratory.		

MCH = mean corpuscular hemoglobin, MCV = mean corpuscular volume.

^aLocal urine testing will be standard for the protocol unless serum testing is required by local regulation or IRB.

2.4.3.4 Physical Examination, Height, and Body Weight

A physical examination including a thorough skin examination will be conducted by the investigator at the Screening and Baseline Visits to ensure that the subject does not have conditions that would interfere with participation in the study.

A complete physical examination will include, at a minimum, assessments of the cardiovascular, respiratory, gastrointestinal systems. Height and body weight will also be measured and recorded at baseline. Physical examinations will only be performed at the indicated visits per study schedule of activities. For all other visits during the study, physical examinations will only be performed when there is a complaint from the subject. Clinically significant abnormal findings from the physical examinations after baseline will be reported as AEs; prior to baseline, they will be reported as medical history.

2.4.3.5 Vital Signs

At in person visits at screening, baseline, Day 15, and Day 29, vital signs will be collected. Blood pressure and pulse measurements will be assessed in a sitting position with a completely automated device. Manual techniques will be used only if an automated device is not available.

Blood pressure, pulse measurements, and temperature (to be taken before blood collection for laboratory tests) are strongly recommended to be preceded by at least 5 minutes of rest with the subject in a quiet setting without distractions (eg, television, cell phones).

2.4.3.6 Electrocardiogram

At screening and Day 29/end of treatment (EOT), a single 12-lead electrocardiogram (ECG) with the subject in a supine position will be performed. The ECG is strongly recommended to be preceded by at least 10 minutes of rest with the subject in a quiet setting without distractions (eg, television, cell phones) and before any blood sampling procedures.

2.4.4 Evaluations – PK

Plasma levels of TER-101 on Days 15, 29 will be analyzed and reported in a separate PK report, if topline results indicate a signal for clinical activity or before the samples exceed their stability, whichever comes first.

3 STATISTICAL METHODOLOGY

This plan describes methods planned for the analysis and display of efficacy and safety endpoints.

3.1 GENERAL STATISTICAL CONSIDERATIONS

Descriptive statistics (mean, standard deviation [Std Dev], median, minimum, and maximum) will be used for continuous variables; number and percentage of subjects will be used for discrete variables. In general, the last measurement prior to the first dose of study treatment will be used as the baseline value with exception of WI-NRS, where the score recorded on Day 1 describing the worst itch score 24 hours prior will be used as the baseline. Nominal visits will be used for by-visit summaries and analyses for safety evaluations (i.e., laboratory sampling, physical examinations, vital signs, and electrocardiogram). For efficacy evaluations of EASI, IGA, and TBSA, analysis visits will be used for by-visit summaries. Analysis visits are defined as below:

Analysis Visit*	Target Day	Range
Day 8	Day 8	Day 2 – Day 11
Day 15	Day 15	Day 12 – Day 21
Day 29	Day 29	≥Day 22

* If there are multiple observations in the range, then the record collected closest to the target day will be selected; if there are multiple observations that have equal distance from the target day, the latter one will be used.

All treatment group comparisons will be made at the 0.05 level using a two-sided hypothesis test, unless otherwise specified. Given the exploratory nature of this study, p-values from all significance tests will be reported without adjustment for multiplicity.

Summaries will be presented by each treatment group, ie, TER-101 2.75% ointment, Vehicle ointment.

All tabulations of summary statistics, graphical presentations, and statistical analyses will be performed using SAS[®] Version 9.4 or higher.

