4.1.2 Baseline (Day 1)

An interval medical and medication history (or change from Screening Visit) will be obtained at the Baseline Visit. AEs occurring between screening and baseline will be obtained. Vital signs, physical examination, and clinical laboratory tests will be conducted. Clinical laboratory tests obtained within 14 days of the Baseline Visit do not need to be repeated. Interval AD history (or any change from Screening Visit) will be collected at Baseline Visit. A urine pregnancy test will be obtained for females of childbearing potential. The IGA, EASI, and TBSA will be obtained for overall baseline AD severity assessments. Standardized photographs of up to 4 affected areas will be obtained. Subjects who meet the inclusion/exclusion criteria will be randomized to either active or vehicle arm at the Baseline Visit.

Subjects will be instructed on use of electronic diary (e-diary) and WI-NRS tool. Subjects will record their worst itch in the previous 24-hour period daily, with the first assessment at the Baseline Visit. The first dose of study drug will be applied by site staff and the subjects instructed on application. Local tolerability will be assessed pre-dose and 15 minutes after investigational product application. The study medication will be dispensed, along with an e-diary to monitor compliance.

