5.3.1 Use of Cleanser, Moisturizer, and Sunscreen During the Study

Subjects may use their own mild cleanser up to twice daily and bland emollient cream therapy once daily. Site staff should review and confirm the cleanser and emollient are acceptable for use (eg, not mediated) at Screening. Bleach baths are not permitted during the study.

Subjects may apply the approved bland emollient cream therapy to non-involved skin once daily at least 15 minutes after application of investigational product. Emollients should not be used in the 24 hours prior to the Baseline Visit, Day 15, or Day 29.

Sun exposure of treatment areas should be avoided. If the location of the treatment sites makes avoidance of sun exposure not feasible, protective clothing and application of an approved

sunscreen with a sun protection factor (SPF) of at least 15 should be used and should be applied at least 15 minutes after application of study interventions.

Throughout the duration of the study, subjects may use their preferred shampoo and may apply makeup to the face. Cosmetics should be applied at least 15 minutes after study drug application. Makeup should not be used in the 24 hours prior to the Baseline Visit and Day 29 Visit.

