8.3.5 Adherence to Study Agent

Adherence with twice daily application of the study agents will be monitored using an e-diary in which the subject will record date and time of application. The e-diary will be dispensed at the Baseline Visit and collected and reviewed at each visit. Adherence will also be monitored by weighing the medication tubes at the Baseline Visit prior to dispensing the study medication to the subject, and at in person visits on Day 15 and Day 29. If the subject has missed more than 2 or more doses in a 7-day period due to reasons related to noncompliance, then study staff will re-emphasize the importance of medication adherence. If the subject continues to consistently miss doses, other than for treatment hold due to local application site or tolerability concerns as described in [Section 6.2](#), then the sponsor should be notified, and the investigator and sponsor may consider discontinuing the subject for noncompliance, as per [Section 7.1](#). Subjects should also be queried by site staff at in person visits that the investigational product is being applied correctly.

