1 STUDY OBJECTIVES AND SAMPLE SIZE RATIONALE

1.1 STUDY OBJECTIVES

TER-101 is a cytosolic phospholipase A2 alpha (cPLA2 α) inhibitor currently in development for the treatment of inflammatory skin diseases, including atopic dermatitis (AD). This Phase 2a study is to assess efficacy, safety, and tolerability of TER-101 (2.75% weight for weight [w/w]) ointment (TER-101 Ointment) with its vehicle (TER-101 Placebo Ointment) twice daily for 28 days in adult and adolescent subjects with mild to moderate AD. Primary and Secondary Objectives are summarized below.

OBJECTIVES	ENDPOINTS
Primary	

 To assess the efficacy of TER-101 (2.75% w/w) ointment vs. vehicle in subjects aged 12 – 65 with mild to moderate AD 	
Primary Efficacy Endpoints
 
 Percent change in EASI from baseline at Day 29 
Secondary Efficacy Endpoints
 
 Percent change in EASI from baseline over time 
 Percent change in EASI by region (head, trunk, UE, LE) from baseline over time EASI-75, EASI-50 responder analysis over time Absolute change in EASI from baseline over time Change in IGA from baseline over time 
 Change from baseline WI-NRS at Days 15, 29 (WI-NRS captured on e-diary daily) Responder analysis: Reduction of ≥ 3 in subjects with baseline WI-NRS ≥ 4 Change in TBSA affected from baseline over time
Secondary	

 To assess the safety and tolerability of TER-101 (2.75% w/w) ointment vs. vehicle in subjects with AD 	
 Safety: TEAEs, SAEs, VS, ECGs, laboratories 
 Tolerability: Scored by investigator at baseline and post-baseline visits on 4-point scale (0 = none; 3 = severe) to include subscores for erythema, burning/stinging, pruritus.

 To assess systemic exposure to TER-101 (2.75% w/w) ointment after BID treatment for 28 days 	PK: systemic plasma trough levels of TER-101 on Days 15, 29

BID = twice daily; EASI = Eczema Area and Severity Index; EASI-50/75 = 50 or 75% reduction in EASI score from baseline; ECG = electrocardiogram; IGA = Investigator Global Assessment; LE = lower extremities; PK =

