2 STUDY DESIGN SUMMARY

This is a Phase 2a, randomized, double-blind, vehicle-controlled study assessing efficacy, safety, and local tolerability of TER-101 (2.75% w/w) ointment vs. its ointment vehicle topically twice daily in adolescent and adult subjects (age 12 - 65) subjects with mild to moderate AD.

Subjects will be randomized 1:1 to receive either TER-101 (2.75% w/w) ointment or vehicle. Both the subject and the investigator will be blinded to the treatment assignments.

[figure not shown]
The study will include up to a 35-day screening period prior to enrollment/baseline visit and a 28-day active treatment period. Subjects will apply assigned treatment to all areas affected by AD at baseline twice daily throughout the treatment period. If the subject develops new areas of AD, those areas will also be treated. Treatment areas will exclude the scalp, nose, mouth and eyes. Subjects may use bland emollients on non-affected body sites once daily. Rescue medications are not permitted.

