3.6.3 WI-NRS Analyses

Descriptive statistics (n, mean, Std Dev, median, minimum, and maximum) will be provided for the 11-point WI-NRS scale at baseline, Day 15 and Day 28 visits, and its change from baseline at Day 15 and Day 28. A line plot over time of the change from baseline (daily, and weekly average [see intervals specified below]) will be generated. Mean (\pm Std Dev) will be displayed at each time point. Change from baseline WI-NRS scale will also be analyzed using the MMRM model for Day 15 and Day 28 assessments. The model will include fixed effect for study treatment (TER-101 2.75%, vehicle), visit day (Day 15, Day 28), and treatment-by-visit interaction, with visit as the repeating factor, subject within the investigational site as a random effect, and baseline WI-NRS scale as a covariate. The treatment p-value (TER-101 2.75% vs. vehicle), treatment difference, and 95% confidence limits from the model, will be presented.

The proportion of WI-NRS responders (defined by a reduction of ≥ 3 in subjects with baseline WI-NRS ≥ 4) will be analyzed using a logistic regression. The odds ratio, and 95% confidence limits from the model, will be presented. The chi-square test p-value will also be provided. In addition, the number and percentage of subjects who respond during each weekly interval (defined by the maximum reduction between Day 2-Day 8, Day 9-Day 15, Day 16-Day 22, Day 23-Day 28) will be summarized and presented in a bar chart.

All analyses will be based on ES.

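### The itch MMRM tests one diary score on Day 15 and one on Day 28 although itch is recorded daily; weekly means would recover lost precision

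*SAP*

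**What the plan says.** Protocol 8.2.4 and SAP 2.4.2.3 have subjects score worst itch daily in the e-diary on a 0 to 10 scale with 24-hour recall. Recording starts on Day 1, "with the first assessment at the Baseline Visit" (Protocol 4.1.2), so no screening scores exist. SAP 3.1 sets the WI-NRS baseline as a single value, "where the score recorded on Day 1 describing the worst itch score 24 hours prior will be used as the baseline".

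For the test, SAP 3.6.3 states: "Change from baseline WI-NRS scale will also be analyzed using the MMRM model for Day 15 and Day 28 assessments". Baseline WI-NRS is a covariate. The same section uses the remaining diary days only descriptively. Daily values and weekly averages go into a line plot. Responders in four intervals (Days 2-8, 9-15, 16-22 and 23-28) go into a summary and bar chart.

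The analysis-visit windows in SAP 3.1 cover EASI, IGA and TBSA but not WI-NRS.

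The endpoint in SAP 1.1 is "Change from baseline WI-NRS at Days 15, 29 (WI-NRS captured on e-diary daily", and Protocol 3 and 9.4.3 also name Day 29. SAP Section 4, which lists changes to planned analyses, does not mention the move to Day 28.

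**The concern.** Worst itch can be expected to vary from day to day. A single entry carries all of that variation into the tested outcome, while a weekly mean removes much of it. The daily scores are already being collected, so testing one day per time point sets aside information at no saving. SAP 3.6.3 gives no reason for doing so.

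It also makes the analysis fragile to a missed entry. With no WI-NRS window, a subject who skips the Day 15 or Day 28 entry contributes nothing to the MMRM at that time point, even if the neighbouring days are complete. The last visit has a window of ±3 days, so it may fall on Day 26 or 27. If the diary is handed in then, there is no Day 28 score at all.

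At stake is the chance of seeing an itch signal in a small study whose stated purpose (Protocol 9.1) is to judge activity and potential for further study.

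**Working it through.** **Trial size.** SAP 1.2 gives about 60 randomized, 15% drop-out and about 50 completers. Check: 60 × 0.85 = 51, and 50 / 0.85 = 58.8, so 59. The figures agree, and 1:1 allocation gives about 25 completers per arm. The documents state no SD, effect or power for itch.

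**Assumptions (not in the documents).** Set the variance of one daily score to 1. Let r be its reliable share, 0.6 to 0.8. Let ρ be the correlation between a single baseline score and a single end score, 0.4 to 0.5. The treatment effect is taken as constant within the averaging week.

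**Formulae.** With independent daily errors, a 7-day mean has variance m = r + (1 − r)/7. The baseline-adjusted residual variance is:
- single day at both ends (planned): 1 − ρ²
- outcome averaged, Day 1 baseline kept: m − ρ²
- baseline averaged only: 1 − ρ²/m
- both averaged: m − ρ²/m

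**Outcome averaged, Day 1 baseline kept:**

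| r | ρ | m | planned | averaged | ratio |
|---|---|---|---|---|---|
| 0.6 | 0.4 | 0.657 | 0.84 | 0.497 | 0.59 |
| 0.6 | 0.5 | 0.657 | 0.75 | 0.407 | 0.54 |
| 0.7 | 0.4 | 0.743 | 0.84 | 0.583 | 0.69 |
| 0.7 | 0.5 | 0.743 | 0.75 | 0.493 | 0.66 |
| 0.8 | 0.4 | 0.829 | 0.84 | 0.669 | 0.80 |
| 0.8 | 0.5 | 0.829 | 0.75 | 0.579 | 0.77 |

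The SAP's last interval, Days 23-28, has six days. Then m = r + (1 − r)/6. The central case (0.7, 0.5) becomes (0.75 − 0.25)/0.75 = 0.67 and the range 0.56 to 0.80, so the difference is immaterial.

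**Autocorrelated errors.** With lag-1 error correlation 0.5, the error variance of a 7-day mean is (1 − r) × [7 + 2 × Σ(7 − j) × 0.5^j]/49, with j from 1 to 6. The sum is 5.016, so the factor is 17.03/49 = 0.348. In the central case m = 0.7 + 0.3 × 0.348 = 0.804 and the ratio is (0.804 − 0.25)/0.75 = 0.74. Over six days the factor is 14.06/36 = 0.391 and the ratio is 0.76.

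**Averaging the baseline.** Baseline only: at r = 0.6, ρ = 0.5, (1 − 0.25/0.657)/0.75 = 0.83; at r = 0.8, ρ = 0.4, (1 − 0.16/0.829)/0.84 = 0.96. Both ends: 0.37 to 0.76, central 0.54. Most of the gain therefore comes from the outcome side.

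**What this means for the test.** In the central case 50 completers would carry the information of 50/0.657 = 76, or 50/0.739 = 68 with autocorrelated errors. As an illustration, assume a single-day SD of 2.5 and a true difference of 1.5 points, with 25 per arm, two-sided 0.05 and a normal approximation:
- planned: z = 1.5/(2.5 × √0.75 × √(2/25)) = 2.45, power 0.69
- 7-day mean: z = 1.5/(2.5 × √0.493 × √(2/25)) = 3.02, power 0.86
- 7-day mean, autocorrelated errors: z = 2.85, power 0.81

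**The case against.** The strongest defence is that change at single days is the protocol's stated endpoint, WI-NRS is one of several secondary endpoints, and the study is exploratory with no multiplicity control. Weekly means would change what is estimated. That stands, and it limits the weight of the point and is why the single-day analysis should be kept.

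A second objection is that a trailing mean dilutes a benefit that is still growing. This also stands. In the unfavourable case of an effect rising in a straight line from Day 1, the mean of Days 23-28 is centred on Day 25.5 and shows 24.5/27 = 0.91 of the Day 28 effect. Against a residual SD of √0.67 = 0.82 of its planned value, signal to noise still improves by 0.91/0.82 = 1.11. The mean of Days 9-15 is centred on Day 12 and shows 11/14 = 0.79 of the Day 15 effect. Against √0.66 = 0.81, the early time point then gains nothing (0.97). If the effect has levelled off, there is no dilution.

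The documents do not support three stronger readings that a reader might infer:
- **The missing diary run-in is the main defect.** Screening can last up to 35 days and no itch is recorded in it, but a 7-day baseline alone leaves 0.83 to 0.96 of the variance. Exclusion 4a in Protocol 5.2 sets a 1-week washout for topical corticosteroids, so the seven days before Day 1 may be the washout week itself. Screening is also not guaranteed to last seven days.
- **Emollient use differs between baseline and Day 28.** Protocol 5.3.1 says "Emollients should not be used in the 24 hours prior to the Baseline Visit, Day 15, or Day 29" and does not name Day 28. However, emollient is confined to non-involved skin, visits have a ±3-day window and no diary entry time is given. A mismatch is therefore not established, and the rules are the same in both arms.
- **A one-day baseline biases the result through regression to the mean.** That effect occurs within each arm. No itch threshold governs entry (Protocol 5.1), and the MMRM adjusts for baseline. Selection on one score matters only for the subset with baseline WI-NRS of at least 4, and it affects both arms.

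**Conclusion.** The point holds as a loss of precision in the change-from-baseline itch MMRM. On the stated assumptions, testing weekly means would leave about 0.54 to 0.80 of the planned residual variance. The central value is 0.66, or about 0.74 with daily errors autocorrelated at 0.5. These figures depend wholly on assumed reliability and correlation, but a gain appears at every setting tried as long as the effect is roughly constant within the week.

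The randomized comparison as planned is not biased. The responder test is outside this conclusion because SAP 3.6.3 does not give its time point. Because itch is secondary and the study exploratory, this is a worthwhile improvement and does not threaten the trial's main conclusion.

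Separately, Day 28 in SAP 3.6.3 conflicts with Day 29 in the endpoint definitions, and the change is undeclared.

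**What to change.** In SAP 3.6.3, before database lock and unblinding:
- Make the MMRM outcome the mean of the available daily WI-NRS scores in Days 9-15 and Days 23-28, intervals that the SAP already defines, minus the Day 1 score.
- Require a minimum number of entries per interval, for example 4, and treat the interval as missing below that.
- Keep the Day 1 score as the baseline covariate.
- Keep the single-day MMRM as a supportive analysis.
- Reconcile Day 28 with the Day 29 endpoint in the protocol and SAP 1.1.
- List both the weekly mean and any change of day in SAP Section 4.

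The cost is SAP wording and programming, with no new data, visits or subject burden. The price is that the estimate describes a week rather than a day and can be diluted if benefit is still growing, most visibly at the early time point.

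A diary run-in during screening is optional. It needs a protocol change, adds diary burden, gives the smaller gain and may overlap the topical corticosteroid washout week.
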